15.6.2. Study Population

Subject Disposition and Study Population
 
Rescreened Subjects
 
 Screening status and reason for screening failure for a subject who has multiple subject numbers will be unique in the unique subject ID. 
 The screening status of a subject who failed screening but passed rescreening will be ‘enrolled’, and the reason for failure will not be counted. The screening status of a subject who failed more than one screening and never passed will be ‘failed’, and the reason for failure will be derived from the latest failure record. Study population of subjects will be derived from the above unique screening status.

Demographics and Baseline Characteristics
 
Age
 
 GSK standard IDSL algorithms will be used for calculating age where birth date will be imputed as follows: 
 A date and month will be imputed as PPD as it will not be captured. Randomization date will be used as reference date of calculation. 
 If randomization date is missing, screening date will be used. 
Body Mass Index (BMI)
 
 Calculated as Weight (kg) / [Height (m)]²

Demographics and Baseline Characteristics									
Type of Prior ESA									

 For this study, prior ESA dose can be administered in several different ways, which are categorized by GSK drug codes as follows. 									

  
 Prior ESA	CMDRGCOL	
   
 Epoetin	00928302 00928303 00928305	
 
 Epoetin beta pegol	53876201	
 
 Darbepoetin alfa	50520401	
  
		Prior ESA	CMDRGCOL	Epoetin	00928302 00928303 00928305	Epoetin beta pegol	53876201	Darbepoetin alfa	50520401
Prior ESA	CMDRGCOL								
Epoetin	00928302 00928303 00928305								
Epoetin beta pegol	53876201								
Darbepoetin alfa	50520401								

 Dosing route (i.v. or s.c.) is captured in eCRF directly. 									
Prior ESA dose (IU/week) at Baseline									

 During screening, subjects may be receiving ESA in multiple ways, including epoetin i.v. or s.c., darbepoetin alfa i.v. or s.c., or epoetin beta pegol i.v. or s.c. The dose of ESA during the period of 12 weeks prior to randomization will be standardized to obtain a continuous single unit prior ESA dose in terms of epoetin i.v. (IU/week). The standardization will be carried with the following formula based on literature review: 
 For subjects taking epoetin i.v. 
 Standardized mean prior ESA dose (IU/week) = epoetin i.v. dose (IU/week) For subjects taking epoetin s.c. 
 Standardized mean prior ESA dose (IU/week) = (161/113)*epoetin s.c. dose(IU/week): [Besarab 2002] For subjects taking darbepoetin alfa i.v. or s.c. 
 Standardized mean prior ESA dose (IU/week) = 250*darbepoetin alfa dose (µg/week) For subjects taking epoetin beta pegol i.v. or s.c. 
 Standardized mean prior ESA dose (IU/week) = 208*epoetin beta pegol dose (µg/week) Prior ESA dose will be calculated using a weighted mean: 
 Mean prior ESA dose (µg/week or IU/week) $= ([dose]_1 * [frequency]_{1+} + \dots + [dose]_n * [frequency]_n) / \{([duration]_{1+} + \dots + [duration]_n) / 7\}$ 
where
 
 [dose]_n : dose at nth record [frequency]_n = 1 when once daily (QD) [duration]_n = [Prior ESA start date]_{n+1} – [prior ESA start date]_n* 
or
 $[Randomization date] - [prior ESA start date]_n^*$ 
when nth record is the last prior ESA dose
 
*Using “[end date] – [start date] + 1” may be inappropriate because the start date may be identical with the end date in case the dose frequency is once daily or twice daily, etc.
 Prior ESA dose during the period of 12 weeks prior to randomization will be used for calculation. 
 Let the latest record of earlier records than the date of 12 weeks prior to randomization date be the 1st record. If no earlier record than the date of 12 weeks prior to randomization date, let the earliest record be the 1st record. If prior ESA start date of 1st record is earlier than 12 weeks prior to randomization date then dose and duration of 1st record for calculation of prior ESA dose are defined as follows: 
 [dose]₁ = Original dose * [Duration]₁ / Original duration Original dose is dose recorded in 1st record 									

Demographics and Baseline Characteristics

- Original duration = [Prior ESA start date]₂ – [prior ESA start date]₁
or
[Randomization date] – [prior ESA start date]₁
when 1st record is the last prior ESA dose
- [Duration]₁ = [Prior ESA start date]₂ – [Randomization date – 84]
or
84
when 1st record is the last prior ESA dose

Illustration of Standardized Mean Prior ESA calculation (ex: epoetin i.v.)

i) 1st record is not earlier than 12 weeks prior to randomization date

Record#	Visit	Start Date	Dose (IU)	Duration (days)
1	Screening	10Feb2017	750	24
2	Screening	06Mar2017	750	28
3	Screening	03Apr2017	1500	28
-	Day 1	PPD [Randomization Date]	Total dose = 3000	Total duration = 80

Mean prior ESA dose (IU/week) = 3000/(80/7) = 262.5

ii) 1st record is earlier than 12 weeks prior to randomization date

Record#	Visit	Start Date	Dose (IU)	Duration (days)	Duration for calculation	Dose for calculation
1	Screening	03Feb2017	750	30	27 ^[1]	750*27/30 = 675
2	Screening	05Mar2017	750	29	29	750
3	Screening	03Apr2017	1500	28	28	1500
-	Day 1	PPD [Randomization Date]			Total duration = 84	Total dose = 2925

[1] [Prior ESA start date]₂ – [Randomization date – 84] = [05Mar2017] – [06Feb2017] = 27

Mean prior ESA dose (IU/week) = 2925/(84/7) = 243.75

Erythropoietin Resistance Index (ERI) at Baseline

- Calculated as standardized mean prior ESA dose (IU/week) divided by weight (kg) at screening visit and then divided by the achieved Day 1 central laboratory Hgb (g/dL).
- If prior ESA data is missing (e.g. ESA non-user), ERI will not be calculated.

Period of Time on Dialysis at Baseline

- Period of time on dialysis (years) will be defined as follows:
 - (Randomization Date – Date of Dialysis Initiation + 1) / 365.25
 - If Date of Dialysis Initiation is partially missing, follow the same handling as concomitant medications in Section 15.7.2.1.

Exposure
Prescribed Dose and Actual Dose for Daprodustat

 • Prescribed dose will be derived from dose level captured in eCRF. • Actual dose will be derived from dose level associated with a container number in eCRF. Note that unscheduled (additional) bottles will not be taken into account. If a container number is "NA" then actual dose is considered as 0mg. • In principle, actual dose will be the same as prescribed dose except for a case in which inconsistency between a prescribed dose and actual bottle(s) occurs. If such an inconsistency occurs, it may not be possible to determine what dose was actually taken. In these cases, the actual dose may be changed from the prescribed dose to a more plausible value based on the available information (e.g., IRT data).
Prescribed Dose and Actual Dose for Epoetin Beta Pegol

 • Prescribed dose and actual dose will be derived from dose level captured in eCRF.
Extent of Exposure of Daprodustat

 • Subjects who were randomized but did not report a treatment start date will be categorized as having zero days of exposure. • Time on study treatment will be calculated based on the formula: 
 ○ Time on study treatment (days) = [Treatment Stop date] – [Treatment Start date] + 1 day The time on study treatment does not exclude dose interruptions. • Cumulative dose will be based on the formula using actual dose: 
 ○ Cumulative Dose = Sum of ([Exposure Duration] x [Actual Dose]) at Each Visit where Exposure duration = [Treatment Stop date] – [Treatment Start date] +1 day • Subject daily dose (= Cumulative Dose / Time on study treatment) is calculated for each subject using actual dose and the summary statistics are calculated based on the subject average daily dose. • Distribution of the dose level Dose level will be classified into 9 categories; 0 mg (i.e. treatment interruption), 1 mg, 2 mg, 4 mg, 6 mg, 8 mg, 12 mg, 18 mg, 24 mg according to actual dose.
Extent of Exposure of Epoetin beta pegol

 • Subjects who were randomized but did not report a treatment start date will be categorized as having zero days of exposure. • Time on study treatment will be calculated based on the formula: 
 ○ Time on study treatment (days) = [Treatment Stop date] (see Section 15.6.1)– [Treatment Start date] + 1 day The time on study treatment does not exclude dose interruptions. • Cumulative dose will be based on the formula using actual dose: 
 ○ Cumulative Dose = Sum of [Actual Dose] at Each Visit • Subject monthly dose (= Cumulative Dose / Time on study treatment x 30.4375 days) is calculated for each subject using actual dose and the summary statistics are calculated based on the subject average monthly dose. • Distribution of the dose level Dose level will be classified into 8 categories; 0 µg (i.e. treatment interruption), 25 µg, 50 µg, 75 µg, 100 µg, 150 µg, 200 µg, 250 µg according to actual dose.
Treatment Compliance of Daprodustat

 • Treatment compliance of daprodustat will be based on # of tablets and categorized as Under compliance, Compliant, and Over Compliant 
 ○ Calculated compliance < 80% → Under Compliant ○ Calculated compliance ≥ 80% and ≤ 120% → Compliant

Exposure		

 ○ Calculated compliance > 120% → Over Compliant ● Treatment compliance will be calculated for daprodustat as following formula: 
 ○ Compliance (%) = [(Total # of tablets actual taken) / (Total # of tablets planned taken)] * 100 where Total # of tablets actual taken = Sum of (Numbers of Tablets Taken at Each Visit) Total # of tablets planned taken = Sum of [(Dosing Stop Date – Dosing Start Date + 1 day) x Planned # of tablet / day in Each Visit] Planned # of tablet/day is defined as follows according to the protocol: 
 ○ 0 mg → 0 tablet/day (i.e. compliance will not be calculated) ○ 1 mg → 1 tablet/day ○ 2 mg → 1 tablet/day ○ 4 mg → 1 tablet/day ○ 6 mg → 1 tablet/day ○ 8 mg → 2 tablets/day ○ 12 mg → 2 tablets/day ○ 18 mg → 3 tablets/day ○ 24 mg → 4 tablets/day where dose record is derived from prescribed dose. 
 ○ Dosing Start Date and Dosing Stop Date will be defined according to the period for compliance calculation as below 		
Period for Compliance Calculation	Dosing Start Date	Dosing Stop Date ^[2]
0 – 2 Week ^[1]	Treatment Start Date	Day 1 Dosing Stop Date
0 – 4 Week (Cohort 1)	Treatment Start Date	Day 1 Dosing Stop Date
0 – 4 Week (Cohort 3)	Treatment Start Date Week 2 Dosing Start Date	Day 1 Dosing Stop Date Week 2 Dosing Stop Date
2 – 4 Week ^[1]	Week 2 Dosing Start Date	Week 2 Dosing Stop Date
Primary Efficacy Evaluation Period (40 – 52 Week)	Dosing Start Date at each visit from Week 40 to 48	Dosing Stop Date at each visit from Week 40 to 48
Overall	Dosing Start Date at each visit	Dosing Stop Date at each visit

[1] Compliance will not be calculated for Cohort 1.
 
[2] If Dosing Stop Date is missing Treatment Stop Date will be used.
		
Treatment Compliance of Epoetin Beta Pegol		

 ● Treatment compliance of epoetin beta pegol will be based on dosing records (dose per every 2 or 4weeks are captured) and categorized as Under compliance, Compliant, and Over Compliant 
 ○ Calculated compliance < 80% → Under Compliant ○ Calculated compliance ≥ 80% and ≤ 120% → Compliant ○ Calculated compliance > 120% → Over Compliant ● Calculated compliance will be provided to derive compliance category only, not provided for any displays. It will be carried using the following formula: 
 ○ Calculated Compliance (%) = [(Total # of dosing) / (Total # of planned dosing)] x 100 ○ Total # of dosing = Sum of Numbers of dosing records where Prescribed Dose equals Actual Dose ○ Total # of planned dosing = Sum of # of planned dosing of each dosing records ○ # of planned dosing = Duration / 14 (if Frequency = every 2 weeks and Prescribed dose ≠ 0) Duration / 28 (if Frequency = every 4 weeks or Prescribed dose = 0) ○ Duration = Start Date of next dosing record – Start Date 
 ▪ If next dosing record is missing, Treatment Stop Date (see Section 15.6.1)+ 1 day will be 		

Exposure	
used. instead of Start Date of next dosing record.	

 Dosing records included in compliance calculation for each period are as below. 	
Period for Compliance Calculation	Dosing Records
0 – 2 Week ^[1]	First record of Day 1
0 – 4 Week	Day 1 to Week 2 (Day 1 for ESA users in Cohort 1)
2 – 4 Week ^[1]	Day 1 (ESA users) Week 2 (ESA non-users)
Primary Efficacy Evaluation Period (40 – 52 Week)	Week 40 to 48
Overall	All records
[1] Compliance will not be calculated for Cohort 1.	

[figure not shown]
Medical Conditions and Concomitant Medications
Iron Medication

 Although the following iron-containing drugs are collected as iron medication data, they will not be included in the summary of other concomitant medications. 
 GSK drug code: 54909401 (SUCROFERRIC OXYHYDROXIDE; P-TOL).

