15. APPENDICES

15.1. Appendix 1: Protocol Deviation Management and Definitions for Per Protocol Population

15.1.1. Exclusions from Per Protocol Population

A subject meeting any of the following criteria will be excluded from the Per Protocol population:

Number	Exclusion Description
01	Informed Consent in Deviation Category
02	Eligibility Criteria Not Met in Deviation Category
03	Not Withdrawn After Developing Withdrawal Criteria in Deviation Category
04	Wrong study treatment or assignment administered in Deviation Subcategory
05	Randomization procedures (e.g. subject assigned to wrong stratum or subject randomized out of order) in Deviation Subcategory
06	Less than 3 out of 4 scheduled evaluable Hgb values from the primary efficacy evaluation period ¹
07	Subject received prohibited medication for more than 14 days during study period ²
08	Non-compliance with randomized medication (compliance category of under compliant or over compliant) ³ during the primary efficacy evaluation period, based on eCRF randomized medication exposure and compliance forms

NOTES:

[1] Evaluable Hgb values are described in Section 15.6.3.

[2] Prohibited medications include strong inhibitors of CYP2C8 (e.g. gemfibrozil) and strong inducers of CYP2C8 (e.g. rifampin/rifampicin), not include erythropoietin (e.g., epoetin/ darbepoetin alfa/ epoetin beta pegol, excluding epoetin beta pegol supplied by GSK).

[3] See Section 15.6.2; Under compliant: <80%, compliant ≥80% and ≤120%, over compliant >120%

CONFIDENTIAL

201753

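### A missed Week 40 epoetin injection with no dosing record drops out of Week 40–52 compliance, so per-protocol exclusion 08 keeps the subject

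*SAP*

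**What the plan says.** The rule is in SAP Section 15.6.2, under treatment compliance of epoetin beta pegol.

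- Numerator: "Total # of dosing = Sum of Numbers of dosing records where Prescribed Dose equals Actual Dose".
- Denominator: "Total # of planned dosing = Sum of # of planned dosing of each dosing records".
- Planned injections for one record: "Duration / 28 (if Frequency = every 4 weeks or Prescribed dose = 0"), or the duration over 14 for every-2-week dosing with a non-zero prescribed dose.
- Length of a record: "Duration = Start Date of next dosing record – Start Date". For the last record, "If next dosing record is missing, Treatment Stop Date (see Section 15.6.1)+ 1 day will be" used in place of the next start date. Section 15.6.1 sets the stop date of a subject who completes treatment to the Week 52 visit date.
- Records used for the primary efficacy evaluation period: those from Week 40 to Week 48.
- Categories: below 80% is Under Compliant, 80% to 120% is Compliant, above 120% is Over Compliant.

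Section 15.1.1, exclusion 08, removes a subject from the per-protocol population for "Non-compliance with randomized medication (compliance category of under compliant or over compliant") in that period.

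On the source of the two doses, Section 15.6.2 says for epoetin: "Prescribed dose and actual dose will be derived from dose level captured in eCRF". For daprodustat it uses the eCRF dose level for the prescribed dose only and gives the other dose its own source: "Actual dose will be derived from dose level associated with a container number in eCRF".

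**The concern.** The denominator is built from records, not from the calendar. A gap after a record lengthens that record and so adds planned injections. A gap before the first record in the period adds nothing. If the Week 40 injection is missed and no record is entered, the gap extends the Week 36 record, which lies outside the period. The category then depends on where in the period the miss falls, and no reason for that is given.

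At stake is the per-protocol population. Sections 7.1.6 and 7.2.5.1 repeat the MMRM, ANCOVA, tipping point and logistic analyses in it. An under-dosed control arm would tend to have lower Hgb, which moves the difference (daprodustat minus epoetin) towards non-inferiority. A per-protocol rule that keeps such control subjects is weaker where it is meant to protect.

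A second, conditional question is whether the numerator can ever reject a record, since one source phrase serves both epoetin doses.

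**Working it through.** The SAP gives no worked figure for this rule, so there is none to reproduce. The formula was applied directly.

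Assumptions: the subject completes Week 52; dosing is every 4 weeks on nominal days at Weeks 40, 44 and 48; a missed injection leaves no record. The last record runs to Week 52 plus 1 day, so a final 28-day interval counts as 29 days.

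Compliance = counted records ÷ (sum of record durations / 28).

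| Situation | Durations (days) | Planned | Compliance | Category |
|---|---|---|---|---|
| All three given | 28 + 28 + 29 | 85/28 = 3.036 | 3/3.036 = 98.8% | Compliant |
| Week 40 missed | 28 + 29 | 57/28 = 2.036 | 2/2.036 = 98.2% | Compliant |
| Week 44 missed | 56 + 29 | 85/28 = 3.036 | 2/3.036 = 65.9% | Under Compliant |
| Week 48 missed | 28 + 57 | 85/28 = 3.036 | 2/3.036 = 65.9% | Under Compliant |
| Weeks 40 and 44 missed | 29 | 29/28 = 1.036 | 1/1.036 = 96.6% | Compliant |

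In each single-miss row, 2 of 3 injections were given (67%).

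**Visit windows.** Appendix 2 allows ±5 days at these visits. Shifting the dates within that range:

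- Week 40 missed: 56/67 = 83.6% to 56/47 = 119.1%, always Compliant.
- Week 44 missed: 56/95 = 58.9% to 56/75 = 74.7%, always Under Compliant.

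**Denominator started at Week 40.** A missed Week 40 injection becomes 2/(85/28) = 2/3.036 = 65.9%, Under Compliant (58.9% to 74.7% over the same windows). It now agrees with a miss at Week 44 or 48.

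**Every-2-week dosing.** Taking six injections from Week 40 to Week 50, an unrecorded first miss scores 5/(71/14) = 5/5.071 = 98.6%. With the corrected start it scores 5/(85/14) = 5/6.071 = 82.4%, still Compliant. The correction therefore changes the category of a single miss only on every-4-week dosing.

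**Overall compliance as a backstop.** With 13 injections over 52 weeks, one unrecorded miss at Week 40 gives 12/13.036 = 92.1%, Compliant. The overall figure would not flag the subject, and exclusion 08 uses the Week 40–52 figure anyway.

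**Source of the two doses.** The result depends on an eCRF layout that the SAP does not show.

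- One shared item: prescribed always equals actual. Three wrong doses, or one missed dose entered as 0 with the other two given, both score 3/3.036 = 98.8%, Compliant.
- Two separate items: one wrong or zero dose against a non-zero prescribed dose scores 2/3.036 = 65.9%, Under Compliant.

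**The case against.** A reader might infer that wrong or missed control injections score as compliant in general. The SAP does not support that. An unrecorded miss at Week 44 or 48 is flagged. Only a miss at Week 40, or a run of misses starting there, escapes. For wrong doses and doses entered as 0, the claim needs prescribed and actual dose to be one eCRF item. The phrase may name only the source system. The compliance rule treats the two as separate values, comparing them and also branching on a prescribed dose of 0, and exclusion 08 refers to exposure and compliance forms. That branch also means that a 0 µg record can be a planned interruption counted as followed, and not a miss.

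Nor does the SAP say that a missed injection leaves no record. The dose-adjustment illustration in Section 15.6.3 carries rows with dose 0. That objection stands as a condition on the point.

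A reader might also infer that the miss cannot be seen anywhere. Section 7.3.2 summarises dose by visit and mean dose over Weeks 40 to 52, Table 2.75 tabulates epoetin dose by visit with categories for not available and 0 µg, and Listing 14 lists epoetin exposure. The miss is absent from the compliance category, not from the report.

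Other exclusions help in part. If Weeks 40 and 44 are missed as whole visits, fewer than three of four Hgb values remain and exclusion 06 removes the subject; it does not do so for a single missed Week 40 visit. Exclusion 04 can remove wrong-treatment cases recorded as deviations.

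Finally, the non-inferiority conclusion rests on the ITT population, and the documents give no count of affected subjects and no basis for an effect on the Hgb difference. All of this limits the point. None of it repairs the denominator, whose behaviour follows from the stated rule under any eCRF layout.

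**Conclusion.** The Week 40–52 denominator is badly fixed. On every-4-week dosing, a missed Week 40 injection without a record scores 98.2%, Compliant, where the same miss at Week 44 or 48 scores 65.9%, Under Compliant. The categories hold across the ±5-day windows. Exclusion 08 therefore keeps such control subjects. The consequence is confined to the compliance table and the per-protocol analyses; the ITT primary result does not change. The finding assumes a subject who completes Week 52 and a miss that leaves no record, and how often that happens cannot be judged from the SAP.

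The dose-source point is secondary and conditional. The SAP leaves open whether the numerator test can ever fail. It does not establish that wrong doses are counted as compliant.

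**What to change.** In Section 15.6.2, start the epoetin Week 40–52 denominator at the Week 40 visit date, or at the nominal Week 40 date if that visit was missed, whether or not a Week 40 dosing record exists. Time from that date to the first existing record then counts as planned dosing, at the frequency in force before the gap. State that a planned interruption needs a record with prescribed dose 0, so that it is not taken for a miss.

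In the same section, name the separate eCRF items that hold the epoetin prescribed dose and actual dose. IRT data can supply the prescribed dose only if that system holds the assigned epoetin dose. Appendix 2 shows an IWRS call at each visit, but the SAP cites IRT data only as an example for daprodustat inconsistencies.

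The first change costs SAP wording and a small programming change, with no new data collection. The second is wording alone if two eCRF items exist; otherwise it needs another source for one of the doses. A few epoetin subjects may leave the per-protocol set. On every-2-week dosing a single miss stays Compliant at 82.4%.

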15.6. Appendix 6: Derived and Transformed Data

15.6.1. General

Multiple Measurements at One Analysis Time Point

 Subjects having both High and Low values for Normal Ranges at any post-baseline visit for safety parameters will be counted in both the High and Low categories of “Any visit post-baseline” row of related summary tables. This will also be applicable to relevant PCI summary tables. For multiple measurements at Screening and/or Day 1 visit, the screening pass visit record will be used for analysis (See Appendix 3: Assessment Windows)
Study Day

 Calculated as the number of days from Randomization Date: 
 Ref Date = Missing → Study Day = Missing Ref Date < Randomization Date → Study Day = Ref Date - Randomization Date Ref Date ≥ Randomization Date → Study Day = Ref Date - (Randomization Date) + 1
Unique Subject ID

 All subjects have unique subject ID for analyses even if a subject was enrolled after rescreened. Tables/figures/listings will be produced based on unique subject ID. For a rescreened subject, the unique subject ID will be derived from the first-assigned subject number though he or she seems to have different subject numbers in eCRF by screening assessments.
Rescreening Subjects

 For rescreened subjects, data collected in screening-pass visit will be used for analysis. They may have multiple records at Screening and/or Day 1 visit, which associates with a screening-pass visit and screening failure visit(s) Regarding a listing of SAEs in screening period, all pre-therapy SAEs captured in eCRF will be provided including screen failure records of rescreened subjects.
Treatment Start Date

 First randomized treatment start date
Treatment Stop Date - Daprodustat

 Calculated as the latest treatment stop date.
Treatment Stop Date – Epoetin Beta Pegol

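### The missing-date rule for daprodustat compliance applies the end-of-treatment date to any record, so one missing Week 40 or Week 44 stop date can put a fully adherent subject out of the Per Protocol population

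*SAP*

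**What the plan says.** Section 15.6.2 (Treatment Compliance of Daprodustat) divides tablets taken by tablets planned. The numerator is "Total # of tablets actual taken = Sum of (Numbers of Tablets Taken at Each Visit". The denominator is "Sum of [(Dosing Stop Date – Dosing Start Date + 1 day) x Planned # of tablet / day in Each Visit". For the primary efficacy evaluation period the start dates used are "Dosing Start Date at each visit from Week 40 to 48", with the matching stop dates, so three records contribute: Weeks 40, 44 and 48.

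A footnote on the stop-date column, which covers every record and every period in the table, reads "If Dosing Stop Date is missing Treatment Stop Date will be used". Section 15.6.1 defines the daprodustat treatment stop date as "Calculated as the latest treatment stop date".

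Compliance below 80% is Under Compliant and above 120% is Over Compliant. Section 15.1.1 excludes from the Per Protocol population, as criterion 08, "Non-compliance with randomized medication (compliance category of under compliant or over compliant", judged on the primary efficacy evaluation period.

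For epoetin beta pegol the same section uses "Duration = Start Date of next dosing record – Start Date" and turns to the treatment stop date (plus one day) only when there is no next dosing record.

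**The concern.** Filling with the end-of-treatment date makes sense for a subject's last record. For an earlier record it does not: a 4-week interval is extended over all later intervals, which still contribute their own planned tablets. The denominator is inflated although the numerator is unchanged.

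At stake is criterion 08. The Per Protocol population is used to repeat the non-inferiority MMRM, the ANCOVA and the tipping point analysis (section 7.1.6) and the logistic model (section 7.2.5.1). A daprodustat subject could be removed from all four, or kept in them, because of one blank date field. The compliance summary in section 6.2 uses the same derivation.

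**Working it through.** The SAP gives no worked compliance example, so there is no figure of its own to reproduce. The check applies its formula as written.

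**Inputs from the SAP:** the formula, the three records and the footnote (15.6.2); the treatment stop date (15.6.1); the limits of 80% and 120%.

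**Assumptions:** 28-day intervals, one tablet per day throughout, and a treatment stop date equal to the true last day of the Week 48 record.

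**Fully adherent subject, 84 tablets taken:**

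| Missing stop date | Planned tablets | Compliance | Category |
|---|---|---|---|
| none | 28 + 28 + 28 = 84 | 84/84 = 100% | Compliant |
| Week 40 | 84 + 28 + 28 = 140 | 84/140 = 60% | Under |
| Week 44 | 28 + 56 + 28 = 112 | 84/112 = 75% | Under |
| Week 48 | 28 + 28 + 28 = 84 | 84/84 = 100% | Compliant |

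**Intake needed to be classed as compliant:** with the Week 40 date missing, 0.8 × 140/84 = 133.3% of the true plan; with the Week 44 date missing, 0.8 × 112/84 = 106.7%.

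**Over-user, 112 tablets taken:** the true value is 112/84 = 133.3%, Over Compliant. With the Week 40 date missing it becomes 112/140 = 80%, and with the Week 44 date missing 112/112 = 100%. Both are Compliant.

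**Sensitivity to visit timing.** Let T be the length of the whole period. A missing Week 40 date gives T/(T + days from Week 44 to the end); a missing Week 44 date gives T/(T + days from Week 48 to the end). The schedule in Appendix 2 allows ±5 days at each of these visits.
- Week 40 missing: from 84/(84 + 66) = 56.0% to 84/(84 + 46) = 64.6%, always Under.
- Week 44 missing: from 84/(84 + 38) = 68.9% to 84/(84 + 18) = 82.4%. It is Under unless the last interval is no more than a quarter of the period.

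**Sensitivity to a dose change.** If the prescribed tablets per day go from one to two after the record with the missing date, a missing Week 40 date gives (28 + 56 + 56)/(84 + 56 + 56) = 140/196 = 71.4%, and a missing Week 44 date gives (28 + 28 + 56)/(28 + 56 + 56) = 112/140 = 80.0%, just Compliant.

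**Other periods (descriptive only, since criterion 08 ignores them).** For Weeks 0 to 4 in Cohort 1, a missing Day 1 stop date gives 28/364 = 7.7%. For overall compliance over 13 records, a missing Day 1 date gives 364/(336 + 364) = 52.0% and a missing Week 32 date 364/(336 + 140) = 76.5%, both Under. From Week 36 on, the result is above 80%.

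**The case against.** The strongest reply is that the case may seldom or never arise. It needs an interim stop date still missing at analysis, with later records present. Section 3.2 puts the analysis after database cleaning, section 4.1 has possible exclusions reviewed before freeze, and Listings 8 and 15 show Per Protocol exclusions and compliance. A spurious 60% would be visible. The more natural case is a missing last record, where the fill is sensible. All of this bears on how often the error occurs. It does not change what the rule returns when it is applied, and the SAP has no step for overriding it.

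A reader might infer three stronger things, which the SAP does not support.

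- **That untreated gaps escape the denominator.** This holds only if the dosing stop date means the last day a tablet was taken, and the SAP does not define it. The dose-adjustment illustration in section 15.6.3 points both ways: two 0 mg records still run 31 and 30 days, which suggests an interval end, while a Week 4 record runs only 14 days before Week 8.
- **That epoetin subjects with a comparable gap are removed while daprodustat subjects are kept.** Take a Week 44 injection given 21 days late with later visits on schedule. The durations are 49 + 7 + 29 = 85 days, so compliance is 3/(85/28) = 98.8%, Compliant. A wholly missed and unrecorded Week 44 injection gives 2/(85/28) = 66%, but that is a different event. Section 15.6.1 also says the epoetin stop date is not captured, so some difference in method is unavoidable.
- **That the Per Protocol population is wrong.** Only criterion 08 is touched, and only for daprodustat subjects with a missing interim stop date. That group may be empty.

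**Conclusion.** The footnote as written gives a wrong compliance value whenever a daprodustat record other than the last has a missing stop date and a non-zero planned dose. In the period that decides criterion 08, a fully adherent subject falls to 60% (Week 40 missing) or 75% (Week 44 missing) under equal intervals and constant tablets per day. The Week 40 result stays below 80% for any visit timing within the permitted windows. The Week 44 result usually does, but can just reach 80% with a short last interval or a rise in tablets per day. Over-use of 133% can be relabelled as compliant.

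The consequence is limited to the Per Protocol sensitivity analyses and the compliance displays. Primary non-inferiority (ITT) and principal secondary superiority (mITT) do not use compliance. The number of subjects affected cannot be derived from the SAP. The rule should be corrected because the error is certain when the case occurs and is easily avoided.

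**What to change.** Reword the footnote in section 15.6.2: use the treatment stop date only for the subject's last dosing record. For any earlier record with a missing dosing stop date, use the next scheduled record's dosing start date minus one day. This follows the logic already written for epoetin beta pegol. In the examples above the denominator returns to 84, so the adherent subject is at 84/84 = 100% and the over-user at 112/84 = 133.3%. Then derive the compliance categories and criterion 08 from the corrected rule.

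When programming it, check that the treatment stop date does not itself depend on the missing last stop date. If it fell back to the Week 44 record's stop, an adherent subject would be at 84/56 = 150%.

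The cost is one sentence in the SAP and a small change to the derivation, using dates the SAP already uses. Records with a recorded stop date are unchanged. Ending every interval at the next dosing start would redefine compliance for all daprodustat subjects and goes beyond what this defect requires.
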